7. MDGA
8. Hematology and serum chemistries blood samples
9. Clinical Immunology Tests blood sample
10. Blood sample for biomarker analyses
11. Complete pulmonary function tests including lung volumes and DLCO % predicted

15.1.5 Final Post-Discontinuation Visit

Regardless of the number of post-discontinuation visits needed every 28 day ± 4 days following the date of completion of the early discontinuation assessments and procedures as planned for study day 168 (week 24), the final post-discontinuation visit will occur at a time point between what would have been study day visit 168 and study day 196-203 follow-up office visit should the participant have not prematurely discontinued ixazomib study medication. The final post-discontinuation visit will include following assessments and procedures:

1. Directed medical history including review of AEs/SAEs and concomitant medications that have been taken since the preceding visit.
2. Physical examination, including vital signs (blood pressure, heart rate, and respiratory rate) and body weight (in kilograms)
3. If participant is taking background MMF, confirm dose and timing of dosing.
4. mRSS
5. UCLA SCTC GIT 2.0 questionnaire
6. Disease-status scales:
 - a. Mahler TDI
 - b. SHAQ
 - c. PtGA

7. MDGA
8. Hematology and serum chemistries blood samples
9. Clinical Immunology Tests blood sample
10. Blood sample for biomarker analyses
11. Complete pulmonary function tests including lung volumes and DLCO % predicted
12. HRCT chest scan

16.0 STUDY ASSESSMENTS

16.1 Assessments for Safety and Tolerability

Safety outcome measures used will include, but will not be limited to:

- Treatment-emergent AEs
- Treatment-emergent SAEs
- Treatment-emergent treatment-related AEs
- Treatment-emergent treatment-related SAEs
- Treatment-emergent AEs leading to ixazomib dose modifications
- Treatment-emergent AEs leading to early discontinuation of ixazomib
- Treatment-emergent changes in clinical laboratory measures
- Treatment emergent changes in patient vital signs
- Treatment emergent changes in UCLA SCTC GIT 2.0 questionnaire

16.2 Assessments for Clinical Efficacy

16.2.1 ACR CRISS (American College of Rheumatology Composite Response Index for clinical trials in early diffuse cutaneous Systemic Sclerosis) [150]

16.2.2 Additional Assessments for Clinical Efficacy

Additional assessments for clinical efficacy will include:

1. Each of the five individual components of ACR CRISS: mRSS (modified Rodnan skin score), FVC % predicted, HAQ-DI (Health Assessment Questionnaire-Disability Index), PtGA (Patient Global Assessment), MDGA (Physician Global Assessment)
2. DLCO % predicted
3. HRCT chest scan ILD severity using the Goh scoring method [6].
4. Additional patient reported outcome Mahler Baseline/Transitional Dyspnea Index (Mahler BDI/TDI).

17.0 DESCRIPTION OF STUDY MEASURES USED FOR ASSESSMENTS

17.1 Informed Consent

Informed consent will be obtained before any study-related observations, assessments, or procedures take place. For patients who require medication washout, informed consent will be obtained before the start of washout. For patients who do not require medication washout, informed consent will be obtained at the screening visit before any study related assessments or procedures are performed. The results of all study assessments and procedures will be documented in the patient's medical record and recorded for study purposes. Study assessments and procedures to be included with each study visit are described in Section 18.1 Study Assessments by Visit. Study assessments and procedures

to be included with each extension study visit are described in Section 25.2 Extension Study Assessments by Visit.

17.2 Study Measures for the Primary Objective to Assess the Safety and Tolerability of Ixazomib:

17.2.1 Medical History

A complete medical history will include a review of all body systems pertinent to the participant, as well as prior and concomitant medications. A complete medical history will be obtained at the start of the medication washout for participants who require washout because of excluded medications, or during the screening for patients who do not require medication washout. A directed medical history will include a review of AEs/SAEs and concomitant medications that have been taken since the preceding visit. A directed medical history will be performed at screening for participants who go through a medication washout period, at study day 1, and at each subsequent study visit every 28 days (weeks 4-24) and at the concluding follow-up office visit (week 28-29) for participants not proceeding on to the extension study. For the extension study, a directed medical history will be performed at each study visit every 28 days (weeks 24-48) and at the concluding follow-up study day 196-203 (week 52-53) office visit.

17.2.2 Physical Examination and Vital Signs

Physical examinations will include a review of all body systems pertinent to the patient, body weight (in kilograms), and vital signs (blood pressure, heart rate and respiratory rate). Height (in centimeters) will also be measured as part of the physical examination at the screening visit. A physical examination will be subsequently performed at study day 1, at study day 84 (week 12), day 168 (week 24), and at the concluding follow-up study day 196-203 (week 28-29) office visits for participants not proceeding on to the extension study. For the extension study, a physical examination will be performed at study day 84 (week 36), day 168 (week 48), and at the concluding follow-up study day 196-203 (week 52-53) office visits.

If clinically significant abnormalities are observed before or on study Day 1, they will be reported in the patient's medical history. If clinically significant abnormalities are observed after study Day 1, a determination will be made if they are new AEs.

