6.0 STUDY OBJECTIVES

6.1 Primary objective:

To determine the safety and tolerability of ixazomib 4 mg taken orally on days 1, 8, and 15 of a 28-day treatment cycle repeated for 6 cycles when administered to adult patients with scleroderma-related ILD as assessed by:

1. Physical examinations, vital signs, 12-lead ECG, echocardiogram, clinical laboratory tests, and pregnancy tests.
2. UCLA SCTC GIT 2.0 questionnaire [148, 149].
3. Averse event documentation.

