7.2 Rationale for Study Design

This is an open-label safety and tolerability pilot study of oral ixazomib in patients with SSc-ILD. An ixazomib dose of 4 mg orally on days 1, 8, and 15 of a 28-day treatment cycle for 6

cycles will be evaluated. This dose is approved for the treatment of multiple myeloma in combination with lenalidomide and dexamethasone in patients who have received at least 1 prior therapy [143].

A six cycle treatment duration was chosen in light of the improved safety profile of oral ixazomib over the earlier proteasome inhibitors bortezomib given either intravenously or subcutaneously and carfilzomib given intravenously particularly in regard to the potential adverse effect of peripheral neuropathy. The common and expected adverse effects have been shown to manifest most often in the initial months of treatment.

To accommodate current approaches to the treatment of SSc-ILD, the study will include 6 study participants taking a stable oral dose of MMF for at least 3 months with ixazomib added to their ongoing treatment, and 6 study participants not receiving treatment specifically for SSc-ILD at study screening. The maximum dose MMF (≤ 1.5 g BID) in this study is based on the dose most frequently used in patients with SSc-ILD. This is the same dose used in the randomized, double-blind, controlled Scleroderma Lung Study-II (SLS II) study comparing oral cyclophosphamide for 1 year plus 1 year placebo with MMF for two years [152].

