7. MDGA
8. Hematology and serum chemistries blood samples
9. Clinical Immunology Tests blood sample
10. Serum pregnancy test (women of childbearing potential)
11. Blood sample for biomarker analyses

12. Obtain skin biopsies
13. Dispense ixazomib 4 mg capsules for the 4-week cycle number 1 (3 capsules)
14. The first dose of ixazomib for cycle 1 will be taken on study Day 1 during the study visit and observed being taken by a member of the study team.
15. Instruct the participant on taking ixazomib day 8 and day 15 of the first cycle

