18.3.3 Study Day 28 (Week 4) Office Visit (± 4days)

On study day 28 the following assessments and procedures will be performed:

1. Directed medical history including review of AEs/SAEs and concomitant medications that have been taken since the preceding visit.
2. If participant is taking background MMF, confirm dose and timing of dosing.
3. UCLA SCTC GIT 2.0 questionnaire
4. Hematology and serum chemistries blood samples
5. Clinical Immunology Tests blood sample
6. Serum pregnancy test (women of childbearing potential)
7. Blood sample for biomarker analyses
8. Spirometry and DLCO
9. Determine if ixazomib dose modification/interruption for hematologic or non-hematologic AE/SAE is indicated (see 9.2 Ixazomib Dose Modification or Interruption); if so, implement designated dose modification/interruption with clinical laboratory assessments more frequently if indicated for the next treatment cycle.
10. Collect unused ixazomib
11. Dispense ixazomib dosing indicated for the 4-week cycle number 2 (3 capsules)
12. If not interrupted, the first dose of ixazomib (day 1) for the cycle 2 will be taken during the study day 28 visit and observed being taken by a member of the study

team.

- Instruct the participant on taking ixazomib day 8 and day 15 of the second cycle.

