24.5 Safety Analyses

The safety population will be used for the analysis of safety data. Summaries of AEs, deaths, and patient disposition will be presented, comparing patients in the two treatment groups. Study periods will be comprised of the following:

- Entire 24-week study period
- First 12 weeks of treatment
- Subsequent 12 weeks of treatment

Safety measurements will include the following:

- Treatment-emergent AEs
- Treatment-emergent SAEs
- Treatment-emergent treatment-related AEs
- Treatment-emergent treatment-related SAEs
- Treatment-emergent AEs leading to ixazomib dose modifications
- Treatment-emergent AEs leading to early discontinuation of ixazomib
- Treatment-emergent changes in clinical laboratory measures
- Treatment-emergent changes in patient vital signs
- Treatment-emergent changes in UCLA SCTC GIT 2.0 questionnaire

AEs will be mapped to system organ classes and preferred terms in MedDRA. Treatment emergent events are defined as those that start or worsen after the start of study treatment through 28 days after the last dose of study treatment. AEs will be summarized by treatment group, system organ class, and preferred term, and by event severity and the event's relationship to study treatment. At each level of summation, patients will be counted only once, under the greatest severity and strongest study-drug relationship.

Clinical laboratory data will be summarized at each measurement time point and for each patient's final post-baseline measurement in the following ways:

- (1) with descriptive statistics (mean, standard deviation, median, and range) for each

measurement time point;

(2) with descriptive statistics for the change from baseline in the measurements at each post-baseline time point; and

(3) with tables summarizing the frequencies of patients below, within, and above the normal ranges at each time point as compared with baseline. All clinical laboratory values collected during the study will be listed, with values outside the normal ranges flagged for clinical evaluation. Grade 3 and 4 laboratory results will be listed and summarized.

Vital signs will be summarized by group and listed by patient.

Data from the UCLA SCTC GIT 2.0 questionnaire at each assessment time will be summarized descriptively without imputation for missing values.

Concomitant medications will be summarized by treatment group based on mapping to drugclasses and generic terms in the WHO Drug Dictionary.

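### Vital signs are a primary-objective safety measure, yet a participant who stays on ixazomib has at most one scheduled on-treatment reading in the first 12 weeks

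*Combined protocol and SAP*

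**What the plan says.** Section 6.1 opens the list of primary-objective measures with "Physical examinations, vital signs, 12-lead ECG, echocardiogram, clinical laboratory tests, and pregnancy tests". Section 7.2, in justifying six cycles, states: "The common and expected adverse effects have been shown to manifest most often in the initial months of treatment".

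Section 17.2.2 takes vital signs and weight as part of the examination: "Physical examinations will include a review of all body systems pertinent to the patient, body weight (in kilograms), and vital signs". After screening, its schedule is "A physical examination will be subsequently performed at study day 1, at study day 84 (week 12), day 168 (week 24", followed by the post-treatment visit for those who do not enter the extension.

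The visit lists in 18.3 match. Days 1, 84 and 168 carry the examination line. The office visits on days 28, 56, 112 and 140 do not, and days 14, 42 and 70 are laboratory visits. The day 28 and day 56 lists still include the step "Determine if ixazomib dose modification/interruption for hematologic or non-hematologic AE/SAE is indicated".

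Section 24.5 names three study periods, one of them "First 12 weeks of treatment", and lists treatment-emergent changes in vital signs among the safety measurements. A later sentence in that section has vital signs summarized by group and listed by patient.

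**The concern.** The measurement schedule does not fit the protocol's own expectation of when toxicity appears. Three full cycles pass before the first scheduled on-treatment blood pressure, heart rate, respiratory rate or weight, although participants are already in the clinic at weeks 4 and 8.

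What is at stake is how much the vital-sign summary can say. Section 5.0 notes that ixazomib has not been studied together with MMF, and it names gastrointestinal effects and peripheral edema among the overlapping risks. Weight, heart rate and blood pressure bear on both. With one scheduled on-treatment reading per continuing participant, at week 12, a statement about early vital-sign change in either group of 6 would rest on a single time point. It could not describe a change that came and went before then.

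**Working it through.** The plan gives no power or sample-size figure to reproduce (24.2 states that no formal hypothesis testing is planned). The check is a count of scheduled events at nominal dates.

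**Inputs.** Dosing is on days 1, 8 and 15 of each 28-day cycle for 6 cycles (9.1). Cycle 1 starts on study day 1, and later cycles start at the visits on days 28, 56, 84, 112 and 140 (18.3). Visit contents are from 18.3.1 to 18.3.11. The treatment-emergent window runs to 28 days after the last dose (24.5).

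**Baseline.** In 18.3.1 the examination is item 2 and the first dose is item 14. The order suggests that the day-1 reading is taken before dosing, though this is not stated.

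**Doses before the first on-treatment reading.** Planned doses: 6 × 3 = 18. Doses before the day-84 visit: 3 cycles × 3 = 9 (days 1, 8, 15, 28, 35, 42, 56, 63, 70). The first dose of cycle 4 is given at the day-84 visit and is listed after the examination. So 9 of 18 doses come first.

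**Scheduled post-baseline collections through day 84:**

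| Measure | Study days | Count |
|---|---|---|
| Hematology and chemistry | 14, 28, 42, 56, 70, 84 | 6 |
| Adverse event review | 28, 56, 84 | 3 |
| GIT 2.0 questionnaire | 28, 56, 84 | 3 |
| Vital signs, weight, examination | 84 | 1 |

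**Whole 24 weeks.** A completer has 2 scheduled on-treatment readings (days 84 and 168). The last dose is on day 140 + 14 = 154, so the treatment-emergent window closes on day 154 + 28 = 182. The follow-up visit on days 196 to 203 falls after it.

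**With readings added at days 28 and 56.** The first-12-week count becomes 3 (days 28, 56, 84). The first reading then follows 3 doses (days 1, 8, 15) instead of 9. Adding days 112 and 140 as well gives 6 in 24 weeks.

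**Position in the cycle.** Existing readings: 84 − 70 = 14 days and 168 − 154 = 14 days after a dose. Added readings: 28 − 15 = 13, 56 − 42 = 14, 112 − 98 = 14 and 140 − 126 = 14 days. The additions improve number and earliness, not timing within the cycle.

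**The case against.** The strongest reply is that nothing here is inconsistent. Sections 17.2.2 and 18.3 agree, the schedule is a design choice, and section 19.0 calls it a minimum, with further visits as toxicity requires. Weeks 4 and 8 are in-person visits, and nothing stops staff from taking a blood pressure. Under 15.0, a participant who stops early returns within 10 days of the last dose for the day-168 assessments, which include vital signs. These may be the participants most affected by early toxicity.

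Much of this stands, and it rules out several stronger readings that a reader might infer:

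- *That early toxicity would go unseen.* The documents do not support this. Adverse event review, GIT 2.0, two-weekly chemistry including creatinine, and spirometry with DLCO at weeks 4 and 8 all cover the period.
- *That the first-12-week period might hold no reading at all.* This would need a cut at calendar day 84. Section 24.5 states none, and 18.3.7 labels the visit week 12 with a ±4-day window.
- *That 24.5 commits to a 12-week summary of vital signs.* Its period list follows the sentence on adverse events, deaths and disposition, and the vital-signs sentence names no period. The link is a reasonable inference from one section. Physical examination is not in the 24.5 measurement list.
- *That readings two weeks after a dose are the fault to repair.* Readings at the intervening office visits would have the same spacing.

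What the reply does not supply is a planned early reading for everyone. Readings prompted by an event or by stopping treatment come from selected participants and cannot give a group series over time.

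**Conclusion.** The point holds as a modest, inexpensive improvement to the safety schedule. For a participant who stays on treatment there is at most one scheduled on-treatment reading of vital signs and weight in the first 12 weeks, after half of the planned doses (9 of 18), against 3 to 6 collections of the other repeated safety measures in the table. That is thin for a named primary-objective measure in the period when the protocol expects most of the common adverse effects.

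The count covers scheduled readings at nominal dates. It assumes that the Appendix A schedule cited in 19.0, which is not in the text available for review, agrees with 17.2.2 and 18.3. The early-toxicity argument does not by itself call for full examinations at the added visits or for changes to the extension visits.

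**What to change.** In 17.2.2, 18.3.3 and 18.3.5, add blood pressure, heart rate, respiratory rate and body weight to the day 28 and day 56 office visits. Days 112 and 140 (18.3.8, 18.3.9) could be added for an even four-week series, but the early-toxicity argument does not require them. Make the same change in Appendix A.

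In 24.5, state that the day-84 visit, including its ±4-day window, counts in the first-12-week period, and say whether vital signs are summarized by period.

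No new visits or staff are needed, because participants already attend on these days for history, blood tests, spirometry and observed dosing. The cost is a few minutes per visit and slightly more data entry. The change concerns measurement only and leaves dosing and dose-modification rules untouched.

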17.2.3 Clinical Laboratory Tests

All clinical laboratory tests will be performed by Mayo Clinic Laboratory:

- **Hematology:** complete blood cell count with automated differential and platelet count, erythrocyte sedimentation rate (ESR) and C-Reactive Protein (CRP).
- **Serum Chemistry:** albumin, alkaline phosphatase, ALT, AST, bicarbonate, direct bilirubin, indirect bilirubin, total bilirubin, calcium, cholesterol, chloride, creatine kinase (CK), creatinine, triglycerides, glucose, lactate dehydrogenase (LDH), magnesium, phosphorus, potassium, total protein, sodium, urea nitrogen, and uric acid.
- **Clinical Immunology:** serum protein immunoelectrophoresis, quantitative immunoglobulins (IgG, IgA, IgM), and IgG tetanus toxoid titer.

The hematology, serum chemistry, and clinical immunology lab tests will be obtained at screening, study day 1, day 28 (week 4), day 56 (week 8), day 84 (week 12), day 112 (week 16), day 140 (week 20), day 168 (week 24), and at the concluding follow-up study day 196-203 (week 28-29) office visits for participants not proceeding on to the extension study.

Additional lab visits are scheduled day 14 (week 2), day 42 (week 6), and day 70 (week 10) for monitoring hematology and serum chemistry tests between study office visits during the first three ixazomib cycles. For the extension study, hematology and serum chemistry tests will be obtained at study day 28 (week 28), day 56 (week 32), day 84 (week 36), day 112 (week 40), day 140 (week 44), day 168 (week 48), and at the concluding follow-up study day 196-203 (week 52-53) office visits.

Specified clinical laboratory assessments will be obtained more frequently if clinically indicated and in conjunction with other laboratory assessments as required.

- **Pregnancy Test** (women of childbearing potential): serum pregnancy test will be performed at screening, on study Day 1; day 28 (week 4), day 56 (week 8), day 84 (week 12), day 112 (week 16), day 140 (week 20), day 168 (week 24), and day 196-203 (week 28-29) follow-up visit for participants not proceeding on to the extension study. For the extension study, serum pregnancy test will be obtained at study day 28 (week 28), day 56 (week 32), day 84 (week 36), day 112 (week 40), day 140 (week 44), day 168 (week 48), and at the concluding follow-up study day 196-203 (week 52-53) office visits.

17.2.4 12-Lead Electrocardiogram

A 12-lead ECG with a rhythm strip will be done during screening. Bronchodilator use will be prohibited in the 24 hours before ECG testing.

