9.2.2 Hematologic toxicity

9.2.2.1 In the event of absolute neutrophil count $\leq 1000/\text{mm}^3$, ixazomib dose will be managed as follows:

1. Ixazomib administration will be interrupted and paused until the absolute neutrophil count (ANC) is $> 1000/\text{mm}^3$ upon retesting of the CBC weekly or sooner as clinically indicated.
2. G-CSF administration may be considered as clinically indicated.
3. Upon recovery of the ANC $> 1000/\text{mm}^3$, ixazomib administration may resume at the first reduction dose of 3 mg with weekly monitoring of CBC for the remainder of that study cycle until the next study visit. The 3 mg dose should follow the dose cycle schedule for the remainder of that study visit and subsequent study visits unless recurrent ANC $\leq 1000/\text{mm}^3$ occurs.
4. In that instance, ixazomib administration will be interrupted and paused until the ANC has recovered $> 1000/\text{mm}^3$ upon retesting of the CBC weekly or sooner as clinically indicated.
5. G-CSF administration may be considered again as clinically indicated.
6. Upon recovery of the ANC $> 1000/\text{mm}^3$, ixazomib administration may resume at the second reduction dose of 2.3 mg with weekly monitoring of CBC for the remainder of that study cycle until the next study visit. The 2.3 mg dose should follow the dose cycle schedule for the remainder of that study visit and subsequent study visits unless recurrent ANC $\leq 1000/\text{mm}^3$ occurs.
7. In that instance, ixazomib administration will be discontinued. A CBC will be monitored weekly or sooner if clinically indicated until the ANC has recovered to $> 1000/\text{mm}^3$. The participant will be discontinued from the study and will proceed to complete assessments and procedures for early discontinuation (See 15.0 Early Discontinuation).

9.2.2.2 In the event of platelet count $\leq 30,000 \text{ mm}^3$, ixazomib dose will be managed as follows:

- **If thrombocytopenia is asymptomatic or associated with petechiae/bruising without other significant bleeding:**
 1. Ixazomib administration will be interrupted and paused until the platelet count is $\geq 50,000/\text{mm}^3$ upon retesting of the CBC daily and then weekly until the platelet count is $\geq 75,000/\text{mm}^3$.

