25.5 EXTENSION STUDY STATISTICAL METHODS and ANALYSES

25.5.1 Extension Study Safety Analyses

The safety population as per Section 24.1 will be used for the analysis of safety data. Summaries of AEs, deaths, and patient disposition will be presented comparing participants in the two treatment groups, those who are taking background MMF and those who are not taking background SSc-ILD medication.

In addition to the initial study treatment periods as described in Safety Analyses Section 24.5 comprised of the first 12 weeks of treatment, the second 12 weeks of treatment, and the entire 24 weeks of the initial study, additional extension study treatment periods will be included in the safety analyses comprised of:

- the first 12 weeks of the extension study
- the second 12 weeks of the extension study
- the entire 24 weeks of the extension study and
- the combined 48 weeks of the entire study.

Safety measurements will include the following:

- Treatment-emergent AEs
- Treatment-emergent SAEs
- Treatment-emergent treatment-related AEs
- Treatment-emergent treatment-related SAEs
- Treatment-emergent AEs leading to ixazomib dose modifications
- Treatment-emergent AEs leading to early discontinuation of ixazomib
- Treatment-emergent changes in clinical laboratory measures
- Treatment emergent changes in patient vital signs
- Treatment emergent changes in UCLA SCTC GIT 2.0 questionnaire

AEs will be mapped to system organ classes and preferred terms in MedDRA. Treatment emergent events are defined as those that start or worsen after the start of study treatment through 28 days after the last dose of study treatment. AEs will be summarized by titration group, system organ class, and preferred term, and by event severity and the event's relationship to study treatment. At each level of summation, patients will be counted only once, under the greatest severity and strongest study-drug relationship.

Clinical laboratory data will be summarized at each measurement time point and for each patient's final post-baseline measurement in the following ways:

- (1) with descriptive statistics (mean, standard deviation, median, and range) for each measurement time point
- (2) with descriptive statistics for the change from baseline in the measurements at each post-baseline time point; and

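### Safety blood tests are scheduled twice as often in weeks 1-12 as in any later 12-week block, which biases the by-period counts of laboratory-detected AEs toward an apparent fall after week 12

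*Combined protocol and SAP*

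**What the plan says.** Section 17.2.3 schedules hematology and chemistry at Day 1 and at every 28-day visit, the later ones being "day 84 (week 12), day 112 (week 16), day 140 (week 20), day 168 (week 24), and at the concluding follow-up" visit. It then adds: "Additional lab visits are scheduled day 14 (week 2), day 42 (week 6), and day 70 (week 10) for monitoring hematology" and serum chemistry, placed "between study office visits during the first three ixazomib cycles". Sections 18.3.2, 18.3.4 and 18.3.6 confirm these three laboratory visits. Sections 18.3.8 to 18.3.10 and 25.2 schedule none mid-cycle after cycle 3.

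Unscheduled testing is allowed: "Specified clinical laboratory assessments will be obtained more frequently if clinically indicated". After a neutrophil or platelet toxicity, dosing resumes "with weekly monitoring of CBC for the remainder of that study cycle until the next study visit" (9.2.2).

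Section 24.5 divides the study into the whole 24 weeks, the first 12 weeks and the "Subsequent 12 weeks of treatment". Section 25.5.1 adds "the first 12 weeks of the extension study", the second 12 weeks, the whole extension and the combined 48 weeks. At each level of the AE summary a patient counts once. The listed measures include AEs that led to a change of ixazomib dose. Laboratory values, changes from baseline and shifts are tabulated by measurement time point. Grade 3 and 4 laboratory results are to be listed and summarised, with no stated period or time-point basis.

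Section 21.1.1 makes a laboratory finding an AE if it is clinically significant, needs an intervention, or leads to a dose reduction or interruption.

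**The concern.** A once-per-patient count in a period is the proportion with at least one detected event. For findings that only a blood test reveals, that proportion rises with the number of tests and depends on when in the cycle they are taken. Both differ between weeks 1-12 and every later block, and neither 24.5 nor 25.5.1 allows for it.

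Safety and tolerability are the primary objective (6.1), and with 12 patients and no formal testing the descriptive tables are the result. Section 7.2 already expects early toxicity: "The common and expected adverse effects have been shown to manifest most often in the initial months of treatment". An artefact in that direction could be taken as confirmation, and could make later treatment, including the extension, look safer than it is.

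**Working it through.** **1. Scheduled draws after Day 1** (17.2.3, 18.3, 25.2)

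| Block | Study days | Draws | Mid-cycle |
|---|---|---|---|
| Weeks 1-12 | 14, 28, 42, 56, 70, 84 | 6 | 3 |
| Weeks 13-24 | 112, 140, 168 | 3 | 0 |
| Extension, first half | 28, 56, 84 | 3 | 0 |
| Extension, second half | 112, 140, 168 | 3 | 0 |

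Days 14, 42 and 70 fall 6-7 days after the most recent earlier dose; the cycle-end draws fall 13-14 days after it (nominal days). The day 196-203 draw adds nothing to the treatment-emergent count: the last planned dose is on day 154 (cycle 6 starts on day 140, plus 14), and 154 + 28 = 182. If a day-84 draw taken up to 4 days late is assigned to the second period, the count becomes 5 against 4.

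**2. Number of draws alone.** The documents give no event rate, so p, the risk of an abnormality per draw, is assumed and held constant. With independent draws, P(at least one) = 1 - (1 - p)^k, with k = 6 or 3.

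| p | Weeks 1-12 | Weeks 13-24 |
|---|---|---|
| 0.02 | 11.4% | 5.9% |
| 0.05 | 26.5% | 14.3% |
| 0.10 | 46.9% | 27.1% |
| 0.20 | 73.8% | 48.8% |

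At p = 0.10: 1 - 0.9^6 = 0.469 and 1 - 0.9^3 = 0.271, so 12 × 0.469 = 5.62 and 12 × 0.271 = 3.25 patients. Treating the two counts as independent Binomial(12), the later count is lower in 79% of trials, tied in 10% and higher in 11%.

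**3. Correlation within patient.** A beta-binomial model at p = 0.10:

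| ICC | Weeks 1-12 | Weeks 13-24 | Later count lower | Later count higher |
|---|---|---|---|---|
| 0.3 | 29.4% | 20.8% | 60% | 23% |
| 0.6 | 19.4% | 15.8% | 49% | 30% |
| 0.9 | 12.1% | 11.4% | 39% | 35% |

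The bias shrinks as abnormalities persist within a patient and is close to nil at 0.9.

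**4. Timing within the cycle.** Let c be the share of cycles with an abnormality visible mid-cycle, constant throughout, and g the fraction still visible at cycle end. Weeks 1-12 detect 1 - (1 - c)^3; a later block detects 1 - (1 - cg)^3. Expected patients of 12:

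| c | Weeks 1-12 | Later, g = 0 | Later, g = 0.5 | Later, g = 1 |
|---|---|---|---|---|
| 0.05 | 1.71 | 0 | 0.88 | 1.71 |
| 0.10 | 3.25 | 0 | 1.71 | 3.25 |
| 0.20 | 5.86 | 0 | 3.25 | 5.86 |

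For c = 0.10 and g = 0.5: 1 - 0.95^3 = 0.143, and 12 × 0.143 = 1.71.

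**5. Restricting to cycle-end draws.** Three draws stand against three. In the model of step 2 at p = 0.10, both periods give 27.1%, with the later count lower in 41% of trials, tied in 18% and higher in 41%. The directional bias is gone. The restricted display cannot see what recovers before cycle end (g = 0 gives 0 in both periods), so mid-cycle events must still be reported.

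**The case against.** **The plan compares treatment groups, not periods.** Section 24.5 compares patients with and without background MMF, who share one laboratory schedule, so that comparison is not biased by it. This stands. But the plan still presents results by period, and readers will compare adjacent columns.

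**Laboratory tables are by time point.** This stands too. A reader might infer that shift tables and mean changes are distorted. They are not, because days 14, 42 and 70 appear there as separate time points. The problem is confined to AE-by-period summaries and, depending on its unstated basis, the grade 3/4 summary.

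**Later testing is not limited to the schedule.** Clinically indicated tests, and closer monitoring after a toxicity or dose change, can catch later events. But they need a trigger, and an asymptomatic abnormality that nobody has measured provides none. The offset is partial.

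**A later fall could be real.** Under 9.2, toxicity leads to dose reduction or discontinuation; 9.3.1 bars a return to the higher dose; and only patients still taking ixazomib enter the extension (25.1). The constant rate used above isolates the artefact and is not a forecast. The plan's tables could not separate the two causes.

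**Recovery by cycle end is not documented.** This stands. A reader might take the half-life of 3.3-7.4 days in section 5.0 as evidence that counts recover in the two drug-free weeks. It describes drug concentration after a dose of 0.48 mg/m², not platelets, neutrophils or liver tests, and the documents do not say when these reach their worst values.

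**Conclusion.** The point holds as a directional bias. Unequal scheduled testing (6 draws against 3, with mid-cycle draws only in cycles 1-3) pushes period summaries of laboratory-detected AEs, and of laboratory-triggered AEs leading to dose changes, toward an apparent fall after week 12.

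The bias is large for transient, asymptomatic abnormalities and near nil for persistent ones. At 10% of cycles, it runs from 3.25 against 0 patients to no difference. These figures assume a constant true rate, 12 patients in both periods, independent cycles and no unscheduled detection.

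A reader might go further and conclude that laboratory toxicity is bound to appear to fall, or to vanish after week 12. The documents do not support that. It would require every abnormality to resolve by cycle end with none caught by an unscheduled test. With moderate persistence (ICC 0.6, p = 0.10) the later count is lower in only about half of trials. Nor would an observed fall be an artefact by default, given the dose-reduction rules.

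**What to change.** In 24.5 and 25.5.1:

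- Keep the full AE-by-period tables, so that no mid-cycle event is lost, with a footnote giving the scheduled draws in each period.
- Add one between-period display of laboratory-detected AEs and grade 3/4 laboratory results restricted to the cycle-end draws common to all periods: days 28/56/84, days 112/140/168 and the corresponding extension visits. Assign draws by scheduled visit, so that a late day-84 draw stays in the first period.
- Count in that display any abnormality present at a cycle-end draw, even if first seen mid-cycle. Otherwise persistent early events would drop out and the bias would reverse.
- Show separately the events detected on days 14, 42 and 70 and those found at unscheduled draws.
- State the basis of the grade 3/4 summary, and rest any statement about the timing of laboratory toxicity on the restricted display.

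The cost is a few sentences, one extra table, and a flag on each laboratory AE for the date of the draw that detected it. No new visit or blood draw is needed. One limit remains: if a mid-cycle finding in cycles 1-3 prompts a dose change and resolves by cycle end, the restricted display will miss it, which is why the separate listing matters.
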